9.11.2 Central Laboratory Tests

Samples for PK, ADA, cytokine, and PD assays are collected per [Appendix 2](#). These assays are performed in a central laboratory designated by the sponsor.

9.11.3 Sample Collection, Storage, and Shipping

Details on laboratory specimen processing, storage, and shipping are provided in the laboratory manual.

9.12 Electrocardiography

Twelve-lead ECGs including QTc interval are assessed per [Appendix 1](#). To account for intrinsic variability, ECGs are obtained in triplicate (3 ECGs per time point at approximately 1-minute intervals).

9.13 End of Study

The EOSV occurs after the last dose of study drug(s) and completion of the follow-up period per [Appendix 1](#). If a participant is unable to complete the study, but has not withdrawn consent, the EOSV is conducted 30 days (+3 day window) after the last dose of study drug.

10 ASSESSMENT OF PHARMACOKINETICS AND PHARMACODYNAMICS

10.1 Pharmacokinetic Assessments

Serum concentrations of study drug(s) will be assessed using quantitative validated bioanalytical methods. Single-dose and multiple-dose PK parameters will be derived from serum concentration versus time data. These parameters may include maximum concentration (C_{max}), time to maximal concentration (T_{max}), area under the concentration-time curve for a dosing interval (AUC_{tau}), trough concentration (C_{trough}), clearance (CL), volume at steady state (V_{ss}), and terminal half-life ($t_{1/2}$).

Analysis of PK data will be performed using industry standard software. Population PK analyses may be conducted using data from this study alone or combined with data from other sponsor-conducted studies.

10.2 Immunogenicity Assessments

Incidence of ADA to study drug(s) will be assessed using validated bioanalytical methods.

10.3 Pharmacodynamic Assessments

The PD samples are prospectively collected and retrospectively analyzed.

10.3.1 Serum Cytokines

Serum samples will be analyzed for concentrations of serum cytokines, including but not limited to IFN- γ , IL-2, IL-5, IL-6, IL-10, and TNF- α .

10.3.2 T-Cell Binding

Peripheral blood samples will be analyzed using flow cytometry to determine the percentage of study drug bound to CD4 and CD8 T cells.

10.3.3 T-Cell Phenotype and Function

Peripheral blood samples will be analyzed using flow cytometry to determine the expression of cell surface markers of T-cell activation and exhaustion. Functional changes in circulating CD8 T cells may also be assessed.

10.3.4 Persistent Human Immunodeficiency Virus-1

Measurements of persistent HIV-1 may include the following:

- Changes in pre- and post-dose measurements of the frequency of resting CD4+ T-cell infection by quantitative viral outgrowth assay (QVOA) in participants who complete the optional leukapheresis.
- Changes in pre- and post-dose measurements of the frequency of resting CD4+ T-cell infection by intact proviral DNA assay (IPDA).
- Changes in pre- and post-dose measurements of the level of resting CD4+ T-cell-associated HIV-1 gag RNA (rca-RNA).
- Changes in pre- and post-dose measurements of levels of residual low-level HIV-1 viremia quantified by single copy assay (SCA).

Although exposure to DART molecules in this study is brief, and latency reversing agents are not included in the experimental intervention at this time, there is a possibility that some persistently infected cells may be depleted. Exploratory assays are limited by blood volumes and the practical considerations of apheresis, but sufficient samples will be available to assess changes in IPDA, rca-RNA, and SCA. When possible, QVOA will be measured. In our experience, performing multiple assays, when possible, is desirable, given the biological and assay variations of these assessments.

11 ASSESSMENT OF EFFICACY

Not applicable.

12 ADVERSE EVENT REPORTING AND ASSESSMENT OF SAFETY

The safety assessment is based on evaluation of AEs occurring from the first administration of study drug(s) through the EOSV or 30 days after the last dose of study drug(s), whichever is later. The safety assessment is based on signs, symptoms, physical examination findings, and laboratory test results.

12.1 Definitions

12.1.1 Adverse Event

An AE means any untoward medical occurrence associated with the use of a drug in humans. AEs may or may not be drug related. An AE is:

- Any unfavorable and unintended sign, symptom or disease temporally associated with the use of a medicinal product.
- Any medical occurrence that is new or has increased in severity or frequency from the baseline condition.
- Any abnormal results of diagnostic procedures, including laboratory test abnormalities.

12.1.2 Adverse Drug Reaction

An adverse drug reaction is a noxious and unintended response to the medicinal product related to any dose. The phrase “response to a medicinal product” means that a causal relationship between a drug and an AE is at least a reasonable possibility.

12.1.3 Adverse Event of Special Interest

An adverse event of special interest (AESI) is a noteworthy event that a sponsor may wish to monitor carefully. It could be serious or non-serious and could include events that might be potential precursors or prodromes for more serious medical conditions in susceptible individuals.

Currently, there are no protocol-specified AESIs for MGD020 or MGD014 in this study.

12.1.4 Serious Adverse Event

An SAE is any AE that results in any of the following outcomes:

- Death
- Life-threatening (immediate risk of death)
- Inpatient hospitalization for longer than 24 hours or prolongation of existing hospitalization (even if the event is Grade 1)

- Persistent or significant disability or incapacity
- Congenital anomaly/birth defect
- Important medical events

12.1.5 Assessment of Causality

Assessment of causality is a determination that describes the relationship or association of the drug with an AE.

This assessment of causality is made by the investigator based on 1) temporal relationship of the event to the administration of study drug; 2) whether an alternative etiology has been identified, and 3) biological plausibility.

Causality assessments that are considered **not related** to study drug:

- *None*: The event is related to an etiology other than the study treatment. An alternative etiology should be documented in the participant's medical record.
- *Unlikely*: The event is unlikely to be related to the study treatment and likely to be related to factors other than study treatment. An alternative explanation is more likely (e.g., concomitant drugs, concomitant disease), or the relationship in time suggests that a causal relationship is unlikely.

If an SAE causality assessment is “unlikely” or “none”, the investigator should document the likely causative mechanism for the event.

Causality assessments that are considered **related** to study drug:

- *Possible*: There is a temporal association of the event with the administration of the study drug. There is a plausible mechanism for relationship to the study drug. However, there is an alternative explanation, such as the participant's clinical status or underlying disease.
- *Probable*: There is a temporal association of the event with the administration of the study drug. There is a plausible mechanism for relationship to the study drug. There is no other reasonable explanation.
- *Definite*: There is a temporal association of the event with the administration of the study drug. There is a plausible mechanism for relationship to the study drug. Causes other than the study drug are ruled out, or the event re-appeared on re-exposure to the study drug.

12.1.6 Severity Criteria

Severity of AEs is assigned per investigator assessment using the DAIDS grading table, corrected version 2.1: <https://rsc.cdc.gov/clinical-research-sites/daids-adverse-event-grading-tables>

Severity Grade for Adverse Events Not Identified in the Grading Table:

The functional table below should be used to grade the severity of an AE that is not specifically identified in the DAIDS version 2.1 grading table.

ADVERSE EVENT	GRADE 1 MILD	GRADE 2 MODERATE	GRADE 3 SEVERE	GRADE 4 POTENTIALLY LIFE-THREATENING	GRADE 5 FATAL
Clinical adverse event not identified in the DAIDS version 2.1 grading table	Mild symptoms causing no or minimal interference with usual social and functional activities with intervention not indicated	Moderate symptoms causing greater than minimal interference with usual social and functional activities with intervention indicated	Severe symptoms causing inability to perform usual social and functional activities with intervention or hospitalization indicated	Potentially life-threatening symptoms causing inability to perform basic self-care functions with intervention indicated to prevent permanent impairment, persistent disability, or death	Death

12.2 Adverse Event Collection and Documentation

12.2.1 Adverse Events

AEs and SAEs will be collected from the time the participant consents to study participation. AEs and SAEs reported between the time the participant signs the informed consent form and administration of the first dose of study drug will be captured as concurrent medical history unless the events are attributed to protocol-specified procedures.

Events attributed to protocol-specified procedures will be collected on the AE eCRFs and SAE Report Form, as appropriate.

AEs, regardless of seriousness, severity, or relationship to study drug(s), are documented in the source and the eCRF, including:

- Duration, severity, and seriousness of each AE.
- Action taken with respect to the study drug(s).
- Investigator's attribution/causality assessment.

- Any medications used to treat the AE.
- Outcome of the event.

A diagnosis should be recorded when signs and symptoms are due to a common etiology (e.g., cough, runny nose, sneezing, sore throat, and head congestion should be reported as "upper respiratory infection"). All treatment measures for AE management will be recorded. All non-serious AEs should be entered into the eCRFs within 10 days of study site awareness.

Clinical Laboratory Changes: Clinical laboratory test results are evaluated by the investigator for clinical significance. The investigator is responsible for reviewing the results of all laboratory tests in a timely manner. The investigator may repeat the laboratory test or request additional tests to verify the results of laboratory tests.

Clinically significant laboratory abnormalities are reported as AEs. A laboratory abnormality is considered clinically significant if it is associated with study drug discontinuation, study drug dose reduction or delay, requires an intervention, or it is suggestive of disease or organ toxicity.

Laboratory abnormalities associated with a diagnosed AE are not reported as separate AEs. For example, report renal failure or hematuria, not the laboratory abnormality (e.g., elevated creatinine or urine red blood cells increased).

The sponsor reports all suspected unexpected serious adverse reactions (SUSARs) to the regulatory authorities and the investigator. The investigator must report SUSARs to the IRB of record as required by the site's institutional policy.

If reporting to the regulatory authorities such as FDA or IRB is required, a copy of the report will also be sent to the NIAID Program Officer or Contracting Officer's Representative, per the NIAID Clinical Terms of Award (<https://www.niaid.nih.gov/grants-contracts/niaid-clinical-terms-award>).

For this study, the participant must be provided with a "wallet (study) card" and instructed to carry this card with them for the duration of the study indicating at least the following:

- Study number
- Statement that the participant is participating in a clinical study
- Investigator name and 24-hour contact telephone number
- Participant number

12.2.2 Serious Adverse Events

All SAEs, regardless of causality, occurring from first administration of study drug through 30 days after the last dose of study drug must be reported to the sponsor. SAEs related to study drug(s) may be reported at any time. The investigator must report the SAE to the sponsor.

- **Within 24 hours** of becoming aware of an SAE, the investigator should send the sponsor a completed SAE Report form by email, or fax, The SAE Report Form and Completion Guidelines, and Contact Information for Reporting SAEs, are provided by the sponsor. Upon receipt of SAE follow-up information, a follow-up SAE Report form should be submitted within 24 hours of becoming aware of the follow-up information. SAEs should be entered into the eCRFs within 5 calendar days of the site's awareness.
- The investigator must follow all SAEs until resolution and record the date of resolution. Resolution of an event is defined as the return to pre-treatment status or stabilization of the condition with the expectation that it will remain chronic. Unresolved SAEs must be followed until:
 - The event resolves.
 - The event stabilizes.
 - The event returns to baseline, if a baseline value/status is available.
 - The event can be attributed to etiology other than the study drug or to factors unrelated to study conduct.
 - It becomes unlikely that any additional information can be obtained (participant or health care practitioner refusal to provide additional information, lost to follow-up after demonstration of due diligence with follow-up efforts).
- Any event requiring hospitalization (or prolongation of hospitalization) that occurs during the study must be reported as a SAE, except:
 - A standard hospitalization for administration of the study drug.
 - A procedure for protocol/disease-related investigations (e.g., surgery, scans, endoscopy, sampling for laboratory tests, bone marrow sampling, pharmacokinetic or biomarker blood sampling).
 - Hospitalizations not intended to treat an acute illness or AE (e.g., social reasons such as pending placement in long-term care or hospice facility).
 - Surgery or procedure planned before entry into the study (must be documented in the eCRF).
- Any SAE of suspected transmission of an infectious agent via a medicinal product will be reported.

12.2.3 **Pregnancy**

All pregnancies in IOCBP participants or IOCBP partners of male participants must be reported to the sponsor. The pregnancy exposure form is sent to the sponsor within 24 hours of study site awareness. The reporting period is from consent through 24 weeks after the last dose of study drug. Abnormal pregnancy outcomes (e.g., spontaneous abortion, fetal death, stillbirth,

congenital anomalies, ectopic pregnancy) are considered SAEs, and reported according to the method in **Section 12.2.2**. Participants with a positive pregnancy test result at any time during the study must discontinue study drug(s).

The investigator must attempt to follow the pregnancy to term or termination and report the outcome and health status of the mother and child. The investigator should discuss with and encourage the pregnant partner to allow collection of follow up information. The pregnant partner information release form must be signed prior to collecting follow-up information. Follow-up information will be collected for all live newborns at birth and 6 months after birth. Information will be collected to assess study drug effects on the newborn. If appropriate, follow-up will be extended.

12.2.4 Other Reporting Situations

12.2.4.1 Adverse Events of Special Interest

Currently, there are no protocol-specified AESIs for MGD020 or MGD014 in this study.

12.2.4.2 Study Drug Overdose

Overdose is administration of a dose of study drug $\geq 20\%$ above the assigned dose. An AE related to study drug overdose must be reported to sponsor within 24 hours of awareness.

12.2.4.3 Product Quality

Any suspected transmission of an infectious agent via a medicinal product or other product quality issue that results in an event of clinical consequence are AEs. The product quality issue must be reported within 24 hours of awareness of the event. See **Section 13** for product quality complaint handling.

12.2.4.4 Discontinuation of Study Drug Due to an Adverse Event

Any AE resulting in the study drug discontinuation must be reported to the sponsor within 24 hours. Follow up of AEs resulting in study drug discontinuation will continue until resolution or stabilization of the AE, unless the participant withdraws consent for further follow up, or until the EOSV. For SAEs, refer to **Section 12.2.2** for follow-up requirements.

13 PRODUCT QUALITY COMPLAINT HANDLING

A product quality complaint (PQC) is defined as any suspicion of a product defect related to manufacturing, labeling, or packaging, i.e., any dissatisfaction relative to the identity, quality, durability, or reliability of a product, including its labeling or package integrity. A PQC may have an impact on the safety and efficacy of the product. Timely, accurate, and complete reporting and analysis of PQC information from studies are crucial for the protection of participants, investigators, and the sponsor, and are mandated by regulatory agencies worldwide. The sponsor has established procedures in conformity with regulatory requirements worldwide to ensure appropriate reporting of PQC information; all studies conducted by the sponsor or its affiliates will be conducted in accordance with those procedures.

All PQCs must be reported to the sponsor within 24 hours of awareness of the event.

If the product defect results in an SAE, the study-site personnel must report the PQC to the sponsor according to the SAE reporting timelines (refer to **Section 12.2.2**, SAEs). A sample of the suspected product should be maintained under correct storage conditions for further investigation if requested by the sponsor.

The name(s) and corresponding telephone numbers of the individuals who should be contacted regarding PQC issues are listed on the contact information page, which is provided as a separate document.

14 STATISTICAL ANALYSIS

This section outlines the statistical methodology and principles which will be used for data analysis in this study. A statistical analysis plan and statistical programming plan will describe the statistical methods and govern the analysis.

14.1 Determination of Sample Size

The study plans to enroll up to approximately 54 participants in total, including up to 30 in Part 1A, 18 in Part 1B, and 6 in Part 2. The exact number of participants cannot be determined precisely in advance but depends upon the occurrence of DLTs and potential need for expanded cohorts.

The sample size in Part 1A is based on a 1+3 design with 3 planned cohorts (12 participants) and 3+3 design for 3 cohorts (18 participants). The sample size in Part 1B is based on a 3+3 design with 3 planned cohorts (18 participants). Part 2 of the study may enroll up to 6 participants based on a 3+3 design with 1 cohort.

The number of participants is not based on statistical power calculations. No inferential statistics will be calculated. The sample size is considered sufficient to evaluate the primary objective of this study (characterize safety and tolerability of the study drugs).

14.2 Analysis Populations

Study analyses will be performed on the following population:

- **Safety population:** All participants who received at least one dose of either study drug. This population will be used to summarize safety data. This population will also be used to summarize baseline data for PK, PD, and immunogenicity analyses.

14.3 Demographics and Baseline Characteristics

Participant disposition, demographics, baseline characteristics, disease history, and medical history will be summarized using descriptive statistics.

14.4 Study Drug Exposure and Concomitant Medications

Study drug exposure and concomitant medications will be summarized by descriptive statistics. The summary of study drug exposure will include descriptive statistics as well as frequency counts for the number of doses received, the total dose actually administered as well as the total dose intended, and the dose intensity which is calculated as percentage of total dose actually administered divided by total dose intended during whole treatment period.

Concomitant medications are coded using the World Health Organization Drug Dictionary.

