4.1.3 Part 2: Multi-Dose Expansion Cohort: Fixed-Dose of MGD020 and Fixed-Dose of MGD014

Part 2 commences only after an MTD or MAD of MGD020 in combination with MGD014 has been determined in Part 1B. Part 2 is a multi-dose expansion cohort with sequential infusions of a fixed dose of MGD020 in combination with a fixed dose of MGD014 administered Q2W for 3 combination doses over 4 weeks (**Table 3**). MGD020 is dosed at the MTD/MAD determined in Part 1B (i.e., MTD_{1B}/MAD_{1B}). MGD014 is dosed at 300 mcg/kg, as determined from Study CP-MGD014-01.

Up to 6 participants may be enrolled in Part 2 using a conventional 3+3 design. If 2 or more participants in the cohort of 6 participants experience a DLT, enrollment and further dosing of ongoing participants will be suspended pending further assessment of safety data.

Table 3 MGD020 and MGD014 Combination Multi-Dose Expansion Cohort Scheme (Part 2)

Cohort	MGD020 ^a (mcg/kg)	MGD014 (mcg/kg)	Design
1	MGD020 MTD _{1B} /MAD _{1B}	300	3+3

- a The MGD020 dose is determined by the combination MTD or MAD in Part 1B.

Participants who completed Part 1 may be considered for enrollment in Part 2, provided they meet all eligibility criteria, did not experience DLT in Part 1, and do not have detectable ADA against MGD014 and/or MGD020 at the completion of Part 1.

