4.4 Guidelines for Dose Modification

No dose modifications are allowed. A reduction of the infusion rate is allowed during re-challenge for an infusion reaction ([Section 7.1](#)).

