4.4.1 Dose Delays

Hold study drug administration for toxicity, pending assessment, management, and resolution of the AE. If the AE is assessed as unrelated to study drug(s) or does not meet DLT criteria, study drug(s) may be restarted at the previous dose and schedule, after appropriate recovery.

In Part 2, a dose delay of up to 7 days is allowed for drug-related or non-drug related AEs. Refer to [Section 7.1](#) for specific guidance on restarting study therapy after infusion reactions. A dose delay $>$ 7 days due to drug-related toxicity will prompt study drug discontinuation.

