4.5 Study Drug Discontinuation

Administration of study drug(s) may continue as specified in the protocol until any of the following conditions are met:

- Adverse event requiring study drug discontinuation (including DLT)
- Completed dosing per protocol
- Death
- Lost to follow-up
- Investigator decision
- Pregnancy
- Major protocol deviation requiring study drug discontinuation
- Study terminated
- Participant decided to discontinue study drug

- Participant withdrew consent from study

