- e On dosing visits (Day 1, 15, and 29), vital signs are measured pre-infusion; at 15 and 30 min after start of infusion (± 5 min); at end of infusion (EOI) of all study drug(s) (± 5 min); at 15, 30, 45, and 60 min post-infusion of last study drug (± 5 min); then every 60 min (± 10 min) until 6 hours after EOI or until the end of the monitoring period (see [Section 6.5.1](#)), whichever comes first (until 2 hours after EOI on Day 15 and 29). During non-dosing in-person visits, vital signs are assessed once.
- f ECGs are performed in triplicate (approximately 1 min apart). At screening and EOSV, ECGs will be taken at one time point. On dosing visits (Day 1, 15, and 29), ECG is recorded pre-infusion, at EOI of all study drug(s), at 30 and 60 min after EOI of last study drug, and as clinically indicated. ECGs after EOI have ± 10 min window.
- g Assess participants for adverse events. Participants are also instructed to contact the study coordinator or investigator if any signs or symptoms of an AE occur at any time during the study.
- h Optional leukapheresis is performed only after the participant is enrolled in the study. If the participant consents to this optional procedure, a baseline leukapheresis is completed. If a baseline leukapheresis was performed, a second leukapheresis procedure is completed 2 weeks (+2 week window) following the final study drug infusion.
- i Additional and/or more frequent safety laboratory tests may be performed as clinically indicated per the investigator's discretion.
- j Clinical laboratory assessments scheduled for Day 1 can be obtained within 7 days prior to infusion. See [Section 9.11](#) for detailed list of assessments. Indirect bilirubin is required if participant on atazanavir.
- k Day 43 hematology is assessed only for participants undergoing leukapheresis. This hematology assessment is performed within the window for the scheduled leukapheresis.

- 1 Participants of childbearing potential only. Serum pregnancy test is required at screening. Subsequent pregnancy tests may use serum or urine. Results must be reviewed before study drug infusion on Day 1, Day 15, and Day 29. If screening test is performed within 72 hours of first infusion, repeat testing on Day 1 may be deferred.
 - m Reflex HCV PCR viral load test is performed only if positive for HCV antibody.

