4.6 Study Drug Exposure and Concomitant Medications

Study drug exposure, ART, and concomitant medications will be summarized by descriptive statistics. The summary of study drug exposure will include descriptive statistics as well as frequency counts for the number of doses or cycles received, the total dose actually administered as well as the total dose intended, and the dose intensity which is calculated as percentage of total dose actually administered divided by total dose intended during study treatment period.

Duration of study treatment (months) will be calculated as:

- (date decided to discontinue treatment date of first dose + 1)/(365.25/12) for participants who have discontinued treatment.
- (date of data cutoff date of first dose + 1)/(365.25/12) for participants whose treatment is ongoing.

The summary of concomitant medications will include the number and percentage of participants who receive any concomitant medications as well as each concomitant medication by drug class. Concomitant medications are coded using the World Health Organization Drug Dictionary.

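### The planned dose intensity has no time term and leaves intended dose undefined, so in Part 2 late dosing scores 100% and a stop after dose 1 scores 33% or 100%

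*Protocol*

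**What the plan says.** Protocol 14.4 asks for the "dose intensity which is calculated as percentage of total dose actually administered divided by total dose intended during whole treatment period". SAP 4.6 keeps the ratio and words the period slightly differently: "percentage of total dose actually administered divided by total dose intended during study treatment period". Neither document defines that period or says which doses count as intended. Both also call for counts of doses received and for the two totals, administered and intended. SAP 4.6 adds treatment duration in months which, for participants who have discontinued, runs to the date of the decision to stop.

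Part 2 is the only multi-dose part. Protocol 4.1.3 has the combination "administered Q2W for 3 combination doses over 4 weeks", and Table 8 in Appendix 1 places the infusions on Days 1, 15 and 29. On departures from the schedule, Protocol 4.4 says "No dose modifications are allowed", while 4.4.1 says "In Part 2, a dose delay of up to 7 days is allowed for drug-related or non-drug related AEs". Protocol 4.5 lists an adverse event, including a DLT, among the reasons for stopping study drug.

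**The concern.** An intensity is normally an amount per unit of time, and this ratio contains no time. Because the dose amount is fixed, poor tolerability in Part 2 can show in three ways: late doses, incomplete or omitted infusions, and early stopping. The ratio registers incomplete or omitted infusions. It cannot register lateness at all. It registers early stopping only if the denominator is the full assigned course, and the text does not say so.

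Tolerability is part of the primary objective, and Part 2 is where the repeated two-weekly regimen is tested. A table headed dose intensity that shows 100% would be read as delivery on schedule. The adverse event tables listed in SAP 4.8.1 include events leading to withdrawal of study drug but none for events leading to delay, and SAP 4.6 has no summary of delays. Delay is therefore the departure that the planned output shows least directly.

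**Working it through.** The documents state no dose intensity value to reproduce. The schedule behind it does reproduce: Day 1 to Day 29 is 29 − 1 = 28 days, or 4 weeks, as Protocol 4.1.3 says.

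Inputs:
- Ratio as written: 100 × dose administered / dose intended (Protocol 14.4, SAP 4.6).
- Assigned course in Part 2: three doses, on Days 1, 15 and 29 (Protocol 4.1.3, Table 8).
- Dose amount fixed (Protocol 4.4). I assume every infusion that is started is completed.
- Delay of up to 7 days (Protocol 4.4.1). The text does not say whether this applies per dose or in total, or whether later doses shift. I therefore use two schedules: delays carried forward (Days 1, 22, 43) and delays measured from the calendar (Days 1, 22, 36). Visit windows are ignored.
- Interval for a time-adjusted figure: my assumption, since the documents give none. I use the first-to-last-dose span (28 days planned) and that span plus a 14-day final interval (42 days planned).

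**Step 1: the ratio as written.** Three full doses on any dates give 3/3 = 100%. Late and on-time dosing cannot be told apart.

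**Step 2: with a time term.** Relative dose intensity = (dose received / actual days) / (assigned dose / planned days). With three full doses this reduces to planned days / actual days.

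| Dosing days | First-to-last span | Span plus 14 days |
|---|---|---|
| 1, 15, 29 | 28/28 = 100% | 42/42 = 100% |
| 1, 22, 36 | 28/35 = 80.0% | 42/49 = 85.7% |
| 1, 22, 43 | 28/42 = 66.7% | 42/56 = 75.0% |
| 1, 22, 29 | 28/28 = 100% | 42/42 = 100% |

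At the maximum delays the range is 67% to 86%; shorter delays fall nearer 100%. The last row shows a limit of the time-adjusted figure itself: it misses a delay to dose 2 that is made up by Day 29. Delays therefore need their own tabulation.

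**Step 3: early stopping, ratio as written.**
- One full dose: 1/3 = 33.3% against the assigned course; 1/1 = 100% against doses due while on treatment; 1/2 = 50% if dose 2 had already fallen due.
- Two full doses: 2/3 = 66.7% or 2/2 = 100%.

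In a Part 2 cohort of six, one participant moving between 33.3% and 100% shifts the mean by 66.7/6 = 11.1 percentage points, and by more if fewer are enrolled.

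**Step 4: the time-adjusted figure does not replace a fixed denominator.** A participant stopped after one dose has (1/14) / (3/42) = 100% on the 14-day convention, and the first-to-last span is zero days. The two statistics have to be shown together.

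**The case against.** The strongest reply is that little is hidden. Beside the ratio, the same sections report doses received, total dose administered and total dose intended. SAP 4.6 adds treatment duration, SAP 4.8.1 tabulates adverse events leading to withdrawal of study drug, and adverse events leading to discontinuation belong to the primary endpoint in Protocol 3.1. A participant stopped after dose 1 for toxicity appears in those tables whatever the ratio says. A reader might infer that a regimen abandoned for toxicity could pass as well delivered; the documents do not support that.

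Treatment duration could also reveal delay. If it ran to the last dose, it would be (28 + 1)/(365.25/12) = 0.95 months on schedule and (42 + 1)/(365.25/12) = 1.41 months for Days 1, 22, 43. But its end point is the decision to discontinue, and the SAP does not say what that date is for someone who completes all three doses. This part of the reply stands only in part.

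Three other strong readings fail:
- The change from whole to study treatment period does not create the 33%/100% split. The period is undefined in both documents, and either wording allows either reading. The duration formula leans towards time on treatment, but nothing ties it to intended dose.
- Nothing feeds dose intensity into the dose and exposure associations of Protocol 14.5.3. Where exposure-response is spelled out, it uses drug concentrations.
- The text does not say that the ratio is computed per drug, so a reader might fear pooling. At the 30 + 300 mcg/kg of the protocol's own example, one missed MGD020 dose in three would then show (60 + 900)/990 = 97.0%. No passage states that the two drugs are summed.

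Finally, the statistical programming plan, which was not available, may define the denominator and the display by drug. It would not be expected to add a time term to a formula that both documents state without one.

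**Conclusion.** The point holds, at modest size. As defined, the ratio gives 100% to three full but late doses in Part 2, where time-adjusted values at the maximum delays are about 67% to 86%. The lower values, 67% and 75%, require the 7-day allowance to apply to each dose and to carry forward; they should not be quoted as the only result. The undefined denominator is a secondary gap, worth 33% against 100% for a stop after dose 1. That gap alone could be settled in the programming plan.

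The figures assume complete infusions and my two interval conventions. The statistic is descriptive, no escalation or stopping rule names it, Parts 1A and 1B are single-dose, and Part 2 has at most 6 participants. The change is worth making because the label promises something the formula cannot measure, and the correction is cheap.

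**What to change.** In SAP 4.6, mirrored in Protocol 14.4, for each drug separately:

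1. Rename the present ratio percent of planned dose received, and fix its denominator at the full assigned regimen: one dose in Parts 1A and 1B, three doses in Part 2.
2. For Part 2, add relative dose intensity = (dose received / actual days) / (assigned dose / planned days). State the interval convention, for example first to last dose plus a 14-day final interval against 42 planned days, and how participants who stop early are handled. Present it beside item 1.
3. For Part 2, tabulate the number and length of dose delays.
4. Use the same wording for the treatment period in both documents.

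This changes no clinical rule. Protocol 6.6 already requires records of administration, so no new data collection should be needed. The cost is a few sentences and some extra programming. Reported figures will be less favourable for participants who were delayed (item 2) or stopped early (item 1).
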